### 1.1 STUDY DISEASE – PERITONEAL CARCINOMATOSIS

Peritoneal carcinomatosis can occur in a variety of malignancies, including those of gastrointestinal (GI) origin, the genitourinary (GU) tract, and primary peritoneal mesothelioma. It is estimated to affect up to 13-17 % of patients with GI malignancies.[14, 15] Current treatments include systemic chemotherapy and regional therapies, namely as cytoreductive

surgery with hyperthermic peritoneal chemotherapy (CRS-HIPEC). This treatment modality can be associated with significant response and typically requires the expertise found in high-volume performing institutions (including Mayo Clinic Florida) in order to provide the infrastructure essential to performing this procedure. Significant oncologic benefits of CRS-HIPEC have been reported for certain malignancies.[16-19] The categorization of CRS-HIPEC has recently changed by the National Comprehensive Cancer Network (NCCN) from being an investigational approach to being a considered approach for the appropriate patient.[20] Despite these advances, current treatments for peritoneal carcinomatosis still generate heterogeneous responses, and many patients will not benefit from CRS-HIPEC or systemic chemotherapy, or may experience limited responses. As such, additional therapies for carcinomatosis are strongly needed. The relevance of this clinical trial in addressing this current need is the investigation of tumor vessels associated with carcinomatosis as a prognostic and ultimately therapeutic target for treatment.

## 1.2 DIAGNOSTIC INTERVENTION - FLUORESCEIN

Drug Information - Fluorescein is delivered intravenously during the course of this observation. Fluorescein is an FDA approved drug for visual angiography. The package insert is shown in Appendix A. A single dose consists of a 5 mL vial of 25% fluorescein and costs \$3.90.

Fluorescein has a very rare incidence of anaphylactic reaction (1 in 222,000), but a skin-prick test may allow these patients to be recognized.[21] Therefore, any reported sensitivity to fluorescein will be considered an exclusion criteria as well as a positive skin-prick test performed during the routine preoperative visit (at least 1 week prior to surgery). The skin-prick test will be performed at the time of the preoperative visit if the patient decides to enter the clinical trial and signs the informed consent. Patients that are not eligible for the study or do not give consent to participate in the study will not undergo a skin-prick test.

The skin-prick test will be performed by the Principal Investigator using a sterile Duotip® lancet (Lincoln Medical, USA) in 3 separate areas of skin on the forearm. The skin-pricks will include 4 microliters of 10% fluorescein, histamine chloride (10 mg/ml) [positive control], and 50% saline solution [negative control] administered in areas of skin prepped with an alcohol pad. After 30 minutes, the appearance of a wheal greater than 3 mm in diameter is considered a positive test result in the context of the appropriate positive and negative control. If a positive test is noted, the patient will no longer be eligible for this study. For comfort and relief of any skin irritation/pruritis, the patient will be offered an anti-histamine (fexofenadine [Allegra®] 30 mg po x 1) following the skin-prick test if necessary.

The package insert for fluorescein (which is a commonly used agent in the OR and readily available to the anesthesiologist in their PYXIS system and does not require delivery from pharmacy or an order to pharmacy) is attached in the Appendix section.

The fluorescein will be provided by the study. It will be ordered and sent to surgery for the patient at the time of the planned microscopic observation.

### **1.2.1 PRECLINICAL STUDIES WITH FLUORESCEIN**

Murine tumors have been investigated with the use of intravital microscopy in an attempt to evaluate blood vessel characteristics, blood flow patterns, and interactions with immune cell subsets.[1, 7, 9] Fluorescein conjugated to Dextran has been employed for several intravital microscopy studies[1, 22] and allows for a more precise assessment of the tumor vasculature[1, 7].

Preclinical laboratory studies have established that fluorescein can be used to image the microvasculature in B16 mouse melanoma tumors in the similar doses used clinically. Fluorescein is not expected to have a direct intervention on tumor biology. The ability to study tumor microvasculature by using IVM does not require a window chamber, and human IVM techniques have provided highly reproducible and consistent measurements. There have been several published animal studies which have demonstrated IVM of the lymphatic system in addition to blood vessels.[10, 23]

### **1.2.2 CLINICAL STUDIES WITH FLUORESCEIN**

This protocol intends to apply the commonly used intraoperative fluorescent agent, fluorescein, to further characterize blood vessels associated with peritoneal carcinomatosis during the course of CRS-HIPEC. It is anticipated that fluorescein will be readily detectable in the microscopic field of observation following intravenous fluorescein injection. This is expected to be similar to a previous trial NCT01886235, which utilized fluorescein to study the microvasculature of melanoma primary tumors, and an on-going trial that uses fluorescein to visualize vessels associated with sentinel lymph nodes (NCT02857374).

Fluorescein is not expected to have a direct intervention on tumor biology. Fluorescein is routinely used during the course of surgery for a variety of indications (e.g. intraoperative assessment of bowel or organ perfusion, vessel angiography of the retina) and is deemed non-toxic with no long term side effects.

Clinically, fluorescein is most commonly used for ophthalmologic procedures including fluorescein angiography with intravenous injection. Fluorescein angiography is performed by injecting fluorescein sodium dye as a bolus into a peripheral vein. The normal adult dosage is 500 mg, and is typically packaged in doses of 5 mL of 10% or 2 mL of 25%. For pediatric patients, the dose is adjusted to 35 mg per 10 pounds of body weight.[24]

Upon entering the circulation, approximately 80% of the dye molecules bind to plasma proteins, which significantly reduces fluorescence because the free electrons that form this chemical bond are subsequently unavailable for excitation.[25] The remaining unbound or free fluorescein molecules fluoresce when excited with light of the appropriate wavelength. With a molecular weight of 376, fluorescein diffuses freely out of all capillaries except those of the central nervous system, including the retina.

The dye is metabolized by the kidneys and is eliminated through the urine within 24 to 36 hours of administration. During this period of metabolism and elimination, fluorescein has the potential to interfere with clinical laboratory tests that use fluorescence as a diagnostic marker.[26, 27] To avoid any false readings, it may be prudent to schedule clinical lab tests either before the angiogram, or postpone testing for 1 or 2 days to allow sufficient elimination of the dye. Side effects of intravenous fluorescein include discoloration of the urine for 24 to 36 hours and a slight yellow skin discoloration that fades within a few hours. Nursing mothers should be cautioned that fluorescein is also excreted in human milk,[28] for this reason, nursing mothers will be excluded from this study.

Use of fluorescein sodium may be contraindicated in patients with history of allergic hypersensitivity to fluorescein. Although generally considered safe for patients receiving dialysis, one manufacturer of fluorescein suggests using half the normal dose in dialyzed patients.[29] There are no known risks or adverse reactions associated with pregnancy, but most practitioners avoid performing fluorescein angiography in pregnant women, especially in their first trimester.[30-32]

Historically, adverse reactions occur in 5% - 10% of patients and range from mild to severe.[33-39] Anecdotal evidence suggests a lower incidence of reaction in recent years and the first large study conducted in over a decade seems to confirm that, reporting a frequency of adverse reaction of just over 1%. [40] Continued improvements in manufacturing processes and implementation of tighter pharmacopeial standards are credited with this reduction and may lead to lower rates of reaction in the future.[41]

Transient nausea and occasional vomiting are the most common reactions and require no treatment. These mild reactions typically occur 30 – 60 seconds after injection and last for about 1 to 2 minutes. Fortunately, they seldom compromise the diagnostic quality of the angiogram. The incidence of nausea and vomiting seems to be related to the volume of dye and rate of injection. A relatively slow rate of injection often reduces or eliminates this type of reaction but can adversely affect image quality and alter arm-to-retina circulation times. Premedication with promethazine hydrochloride or prochlorperazine may prevent or lessen the severity of nausea and vomiting in patients with a history of previous reactions to fluorescein, but is rarely needed and one study noted a higher frequency of these reactions in patients that had been premedicated.[37] Some patients report a strong taste sensation or hypersalivation following injection of fluorescein.

Moderate reactions occur less frequently, affecting less than 2% of patients that undergo angiography. Allergic reactions such as pruritus or urticaria can be treated with antihistamines, but any patient who experiences these symptoms should be observed carefully for the possible development of anaphylaxis. The advisability of performing angiograms in patients with a history of allergic reaction to fluorescein should be considered carefully, as allergic sensitization to the dye can increase with each subsequent use. Patients with previous history of mild allergic reaction to fluorescein can be pre-treated with an antihistamine, such as diphenhydramine,

30 - 40 minutes prior to any subsequent angiograms to limit allergic response, although this may not prevent serious reactions.[42]

More severe reactions are rare, but include laryngeal edema, bronchospasm, anaphylaxis, tonic-clonic seizure, myocardial infarction, and cardiac arrest.[43-47] The overall risk of death from fluorescein angiography has been reported as 1 in 222,000.[37] Although life-threatening reactions during angiography are rare, angiographic facilities and personnel should be properly equipped and prepared to manage serious reactions to the procedure. A resuscitative crash cart and appropriate agents to treat severe reactions should be readily available including epinephrine for intravenous or intramuscular use, soluble corticosteroids, aminophylline for intravenous use, oxygen, and airway instrumentation. It is generally recommended that a physician be present or available during angiographic procedures.

Extravasation of fluorescein dye during the injection can be a serious complication of angiography. With a pH of 8 to 9.8, fluorescein infiltration can be quite painful. If fluorescein dye extravasates, cold compresses should be placed on the affected area for 5 to 10 minutes, and the patient should be reassessed until edema, pain, and redness resolve. Serious complications are more likely to occur when large amounts of dye extravasate. Sloughing of the skin, localized necrosis, subcutaneous granuloma, and toxic neuritis have been reported following extravasation of fluorescein.[48-50] To avoid these problems, continual observation of the injection site during the course of the injection and monitoring the patient for pain is recommended. Accidental arterial injections are rare, but can be quite painful. The dye remains concentrated and stains the effected extremity with little or no dye reaching the retinal vasculature. With proper technique, these complications of injection can usually be avoided.

### **1.3 RISKS AND/OR BENEFITS**

**Risks** – low risk of reaction to fluorescein as described above. Otherwise, no increased risk of surgical procedure anticipated. There are inherent risks to CRS. Studies have characterized the complications for which patients undergoing CRS-HIPEC are at risk, including anastomotic leak, ileus and obstruction, and neutropenia.[51-53] However, these risks are not expected to be increased due to the use of fluorescein.

**Benefits** – depending upon collected findings and correlation with clinical outcome, IVM may offer prognostic information and contribute to staging classifications for peritoneal carcinomatosis with the intent of potentially guiding treatment decisions in the future.

### **1.4 DIAGNOSTIC INTERVENTION – INDOCYANINE GREEN (ICG)**

Drug Information – Indocyanine green (ICG or IC-Green) is the second intravenous (IV) dye to be administered in this clinical trial. The ICG will be administered after the fluorescein has been observed to washout from the tumor associated vasculature, which can be directly monitored during HIVM. Following this, the ICG will be injected. ICG injection after fluorescein injection is favored due to the characteristics of these dyes, with ICG being heavier and more albumin

bound than fluorescein. ICG would be expected to stay within the intravascular compartment longer than fluorescein with estimates of up to 20-30 minutes. It is therefore a more optimal utilization of time to administer the dyes in this order, because the reverse order (ICG prior to fluorescein) may result in an increased waiting time for the ICG to dissipate from the circulation.

ICG was approved by the FDA in November 2007 for use in the study of cardiac output determination, hepatic function and liver blood flow measurement, and ophthalmic angiography.[54, 55] However, it has been used in many different clinical applications, including those listed above, for over 50 years.

It is supplied by Akorn, Inc. under the brand name IC-GREEN®. In this study, a single unit for a given patient consists of a 25 mg vial to which 5 ml of aqueous solvent (sterile water) is added, thereby reconstituting the drug to 5 mg/ml. Further dilutions are achieved using sterile saline, making the final solution slightly hypo-osmolar.

Administered dosages vary for different investigative purposes. Based on hepatic function studies, the dose to be administered is calculated for 0.5 mg/kg of body weight.[55] The total dose of ICG should not exceed 2 mg/kg. The dose used for the purposes of vessel evaluation have been reported to be much lower (e.g. 0.5 mg - 5 mg per patient).[56] Administration of 5 mg is the recommended dose for cardiac dilution studies for adults.[55] Therefore, it is anticipated that the dose used for this evaluation is well below the maximum recommended dose. The dose of 5 mg ICG would be an appropriate amount for this study.

The drug is supplied as a kit containing six 25 mg vials and six 10 ml Aqueous Solvent ampules. The cost of a single kit is \$508.76.

ICG is an iodide-containing, water soluble tricarbocyanine dye that fluoresces when exposed to infrared light (800 nm).[57] Compared to Fluorescein, the molecular weight of ICG is over double at 774.98 g/mol (Fluorescein molecular weight is 332.31 g/mol). The package insert and the Material Safety Data Sheet are shown in the Appendix B.

Following IV injection, ICG is rapidly bound to plasma proteins of which albumin is the main carrier (95%).[55, 58] The drug undergoes no significant extrahepatic or enterohepatic circulation; it is taken up mainly by hepatic parenchymal cells and excreted into bile.[55, 59] It has a plasma half-life of approximately 3-4 minutes.[55, 58] Due to its high binding to albumin and significantly greater molecular weight than Fluorescein, ICG is expected to persist within the tissues for a longer period of time resulting from a slower washout. This characteristic would have several advantages to the study of HIVM in tumor associated vessels, including increased imaging times, more extensive characterization of blood vessel architecture, and more accurate calculation of blood flow velocities.

The ICG will be provided by the study. It will be ordered and sent to the operating room during surgery at the time of the planned HIVM observation. The dose to be administered will be calculated prior to the surgery based on the patient's most accurate and current weight. It will be

injected through the IV by a physician member of the surgical or anesthesia team. Surgeons and anesthesiologists have experience with the IV administration of ICG during other procedures, such as injection during plastic surgery reconstructive procedures to assess tissue viability.

Similar to Fluorescein, ICG has a rare incidence of anaphylactic reaction (0.05 – 0.15%). It does contain an iodide component, which accounts for the allergy potential of ICG. Therefore, patients with a known allergy to iodine or contrast dye will be excluded from the study. Patients who have received iodine based contrast computerized tomography (CT) scans with IV iodine contrast dyes would be unlikely to have an iodine allergy, particularly if multiple scans have been performed. During the staging of patients with peritoneal carcinomatosis, routine use of imaging is routinely recommended to investigate the degree of metastasis. Thus, it is extremely unlikely that a patient who has received IV iodine contrast dye during a CT scan will have an allergic reaction to ICG.

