#### **1.4.2 CLINICAL STUDIES WITH ICG**

Similar to Fluorescein, ICG is not expected to have a direct intervention on tumor biology. ICG has been used during the course of surgery and other procedures for widespread indications and is FDA approved. In general, it is well tolerated, non-toxic, and has no long term side effects.

Clinically, ICG is most commonly used in the assessment of liver function,[63-65] ophthalmic angiography,[66-68] and the analysis of cardiac function with increasingly novel applications in cardiac studies.[69, 70] It is typically administered by a member of the anesthesia team during cases or procedures in the operating suite under general anesthesia. In addition to these applications, ICG has been used in a variety of other studies in a safe manner. ICG has been used to map sentinel lymph nodes (SLN) in several malignancies,[71] including melanoma,[56, 72, 73] breast,[74-76] and colon cancer.[77] These studies have not reported any major adverse reactions or toxicities resulting from exposure to ICG. While the doses of ICG used in these studies varies, the recommended dose per the manufacturer is calculated on the basis of 0.5 mg/kg of body weight.[55]

Other applications of ICG have been studied in the field of plastics surgery. ICG has been given in patients to determine the perfusion and viability of perforator flaps.[78, 79] Similar to the studies in malignancy and SLN, the fluorescent properties of ICG have been utilized and shown to be effective in other studies. ICG has also been used to identify and target esophageal varices.[80] Further, during neurovascular operations, ICG has been readily administered by

anesthesiologists during intraoperative videography of aneurysm clippings and carotid bypass procedures.[81, 82]

As discussed in the previous section, the use of ICG is contraindicated in patients with a history of allergic hypersensitivity to iodine. There have been rare but reported cases of anaphylaxis and death due to allergic reactions during procedures using ICG.[25, 83, 84] Therefore, patients with a history iodine allergy will be excluded from our clinical trial. Other adverse reactions have been reported with the use of ICG in patients with allergic reactions.[85]

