fluorescence. IVM is continuously performed at the time the fluorescent agent is injected and video is recorded in real-time. The fluorescein is almost immediately visible within the microscopic field, and the vessels are quickly outlined in great detail. The fluorescence lasts for a few minutes (2-3 minutes) and then either fades or begins to permeate through the tissue. The extravasation of dye will be determined by visualizing fluorescence outside of the defined vessels for a total time of 5 minutes. The distance from the vessels will be measured, recorded, and expressed as a function of time (extravasation rate) in an analysis performed off-line from the digitally recorded video.

Following the dissipation of the fluorescein from the visual field, 5 mg of ICG will be injected intraveneously. The observation will repeat in a similar manner, now with the use of ICG. Tumor-associated vasculature will be observed in order to record the similar vessel characteristics. ICG is expected to persist within the vasculature for an extended period of time, thereby allowing further characterization of the field. It is not necessary to wait for the ICG to dissipate from the field as this may take up to 20-30 minutes due to its high level of albumin binding.

At the completion of the observation period with ICG, the microscope will be removed and sterilized between uses. This would complete the observation period, which is anticipated to take 15 - 20 minutes total time. The observation will take place during the course of standard surgery and is not anticipated to delay or significantly lengthen the duration of the procedure. For example, other portions of the procedure will be continued during the observation period (e.g., setting up the circuit required for HIPEC). The tumor implants will be removed and undergo standard pathology evaluation. The patient will recover in the PACU per standard protocol.

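### Section 1.4 calls for an ICG dose calculated from body weight but gives no rate for it, while Sections 1.4 and 4.2 also state a fixed 5 mg; the dosing instructions must be reconciled

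*Combined protocol and SAP*

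**What the plan says.** Section 1.4 (Diagnostic Intervention – Indocyanine Green) covers ICG dosing in two places.

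- Its dosing paragraph notes that doses differ by purpose. It then gives a weight-based figure with its context: "Based on hepatic function studies, the dose to be administered is calculated for 0.5 mg/kg of body weight". It sets a ceiling of 2 mg/kg, reports much lower doses for vessel evaluation (0.5 to 5 mg per patient, as examples), and ends: "The dose of 5 mg ICG would be an appropriate amount for this study".
- Its later paragraph on ordering and injecting the dye says: "The dose to be administered will be calculated prior to the surgery based on the patient's most accurate and current weight". No rate is attached. The injection is assigned to a physician of the surgical or anesthesia team.

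Section 1.4.2, a review of earlier clinical use, adds that "the recommended dose per the manufacturer is calculated on the basis of 0.5 mg/kg of body weight".

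Section 4.2 (Study Methods) states at the injection step that "5 mg of ICG will be injected", with no weight adjustment.

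Sections 3.1, 3.3 and 9 make primary success depend on completing every listed item. These include seeing both dyes in the vessels and calculating the tissue penetration of both. Section 4.2 measures dye uptake as distance from the vessel over time and as the percentage of the field in which dye is detected.

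**The concern.** The preparation step in Section 1.4 and the injection step in Section 4.2 are both written as things that will be done. A fixed amount requires no calculation from weight, and a weight calculation does not yield one fixed amount for every patient. Nothing says which text governs, and Section 1.4 disagrees with itself as well as with Section 4.2.

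This matters statistically because ICG detection is part of the primary endpoint. Whether dye is visible, how far it is seen to spread and how much of the field it fills could all depend on how much was injected. Section 9 opens Part II on seven successes in ten, so the classification of a single patient can decide the result. Section 9 also counts failure to detect flow or dye as an abnormal observation, which feeds the between-patient correlations with grade and survival.

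The available text does not ask for the administered ICG dose to be recorded. If two staff members followed different sentences, the analysis would have no way to show it.

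**Working it through.** The plan has no calculation to reproduce: 5 mg is stated as an amount and is not derived from weight. The check is whether the two instructions can agree at any adult weight and, if not, how far apart they could be.

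**Inputs**
- Fixed dose: 5 mg (Sections 1.4 and 4.2).
- Rate for the weight calculation: not given in the sentence that requires it. The only calculation rate in the documents is 0.5 mg/kg (Sections 1.4 and 1.4.2). Using it here is an assumption.
- Ceiling: 2 mg/kg (Section 1.4).
- Body weight: no distribution is given. I assume 50 to 100 kg, with 40 and 120 kg as a wider check.

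**Formulas**
- Weight-based dose = 0.5 mg/kg × weight.
- Ratio = weight-based dose ÷ 5 mg.
- Fixed dose per kg = 5 mg ÷ weight.

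| Weight (kg) | 0.5 mg/kg dose (mg) | Ratio to 5 mg | 5 mg expressed per kg (mg/kg) |
|---|---|---|---|
| 40 | 20 | 4 | 0.125 |
| 50 | 25 | 5 | 0.10 |
| 70 | 35 | 7 | 0.071 |
| 100 | 50 | 10 | 0.05 |
| 120 | 60 | 12 | 0.042 |

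**Can they agree?** Setting 0.5 × weight = 5 gives a weight of 10 kg. The trial enrolls adults, so at this rate no plausible patient receives the same dose under both instructions.

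**Against the ceiling.** 0.5 ÷ 2 = 25% of the stated maximum at any weight. For 5 mg, the fraction is 5 ÷ (2 × 50) = 5% at 50 kg and 5 ÷ (2 × 100) = 2.5% at 100 kg. Both readings lie below the ceiling.

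**What cannot be computed.** The documents give no relation between ICG dose and either visibility or diffusion distance. The change in the success rate from a mixture of doses therefore cannot be derived.

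**The case against.** The strongest reply is that the documents largely settle on 5 mg. The 0.5 mg/kg figure is tied to hepatic function studies, and in Section 1.4.2 it is a report of the manufacturer's recommendation within a literature review. No sentence says that 0.5 mg/kg will be given in this trial. The dosing paragraph moves from that figure to lower doses for vessel work and then names 5 mg for this study, and the methods section repeats it. On this view a single sentence without a rate is out of line. At one center with one methods section, everyone may simply follow Section 4.2, and every patient would then receive the same dose.

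Much of this stands. It means the fold difference is conditional, and that the title of the problem is not Section 1.4 against Section 4.2, because Section 1.4 supports both readings. It also stands that the comparison of tumor with normal peritoneum is made within each patient, so both tissues share one dose and that comparison is less exposed. It does not remove the contradiction: the weight sentence comes after the dosing paragraph, sits in the ordering and injection step, and is written as an instruction.

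Three stronger readings are tempting, and the documents do not support them.

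- *A supply shortfall.* Section 1.4 says "a single unit for a given patient consists of a 25 mg vial", and 25 ÷ 0.5 = 50 kg, so one vial would not cover 0.5 mg/kg above that weight. This is better read as a sign that 0.5 mg/kg was not planned than as a supply defect.
- *Safety rates that pool different exposures.* Section 1.4.2 says that ICG dose has not been well correlated with the severity of symptoms, and both readings are under the stated maximum.
- *A demonstrated bias in the feasibility result.* Without a dose-response relation in the documents, none can be shown.

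**Conclusion.** The concern holds as an internal contradiction in a study procedure. Section 1.4 requires a weight calculation without a rate, while Section 1.4 and Section 4.2 also give a fixed 5 mg, and both cannot be followed. Comparability of the two ICG components of primary success between patients is at risk only if staff act on different sentences in different patients.

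The possible dose gap is 5- to 10-fold over 50 to 100 kg (4- to 12-fold over 40 to 120 kg). That rests on two assumptions: the weight range, and that someone following the weight sentence would use 0.5 mg/kg for want of any other rate. If all staff follow Section 4.2, the gap is zero. The effect on the success rate is unknown. This review takes no view on which dose is right.

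**What to change.** 1. Reconcile the two statements in Section 1.4 and the one in Section 4.2 to a single ICG dosing instruction. The sponsor decides which.
2. State in Sections 1.4 and 1.4.2 that the 0.5 mg/kg figure is background, unless the sponsor adopts it for the trial.
3. Record the ICG amount actually given to each patient, in mg. Section 6.1 already collects body weight at baseline, so mg/kg can be derived without further data, and any patient dosed differently can be identified when the ICG items are read.

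The cost is a wording change in the protocol and one case report form field. No procedure, visit or patient is added.
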